8.10. Imputation of Incomplete Dates

The dates of certain historical or current clinical activities are key component for statistical analysis. An incomplete date results from a missing day, month or year; in that case, the missing figure can be imputed allowing for the calculation of variables, such as duration and time to certain event. However, when all of them, day, month and year are missing no imputation will be done.

Before registration/treatment start

If the day of a month is unknown, then the imputed day will be the 15th of the month; if the month is also unknown, then the imputed date will be the 1st of July. This assumption will only be valid if the imputed date occurs earlier than the first dose administration date; otherwise the imputed date will be the first day of the month in which the first dose was administered (i.e. 01/ first dose administration month date/year).

Between treatment start and end of treatment

All date variables during treatment for which information is needed and is not fully available, for example AEs or concomitant medications, will be subjected to imputation by means of SAS programming. If the day of a date is unknown then the imputed day will be the 1st of the month, if the month and/or year are also unknown then the imputed date will be the 1st of January. This assumption will be valid if the imputed date is earlier than the treatment start date; otherwise, the imputed date will be the treatment start date.

After end of treatment

To ensure the most conservative approach for the time-to-event variables (i.e., DR, PFS and OS), which can be affected by missing values, the following rules will be implemented: if the day of a date is unknown then the imputed day will be the 1st; if the month is also unknown, then the imputed date will be the 1st of July. This assumption will be valid if the imputed date occurs later than the last drug administration date; otherwise the imputed date will be the date of the last drug administration plus the predefined cycle length (i.e., 21 days if PM060184), except if the patient dies before, in which case the date of death minus 1 will be used.

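### The SAP's post-treatment date imputation is checked only against the last dose, so it can place a death outside its recorded month or year, or before a documented later contact

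*SAP*

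**What the plan says.** The paragraph of SAP 8.10 headed After end of treatment opens with its aim: "To ensure the most conservative approach for the time-to-event variables", which it lists as duration of response, PFS and OS. The rule then has four parts.

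- An unknown day becomes the 1st of the month. For the month, "if the month is also unknown, then the imputed date will be the 1st of July".
- There is one validity check: "This assumption will be valid if the imputed date occurs later than the last drug administration date".
- If the check fails, "otherwise the imputed date will be the date of the last drug administration plus the predefined cycle length", given as 21 days for PM060184.
- The fallback has one exception: "except if the patient dies before, in which case the date of death minus 1 will be used".

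SAP 3.3 and 6.1 end OS at death or last contact, and PFS at progression, death or last tumor evaluation. Protocol 7.6 plans follow-up about every three months and lets survival information come by telephone, e-mail or from the chart. SAP 8.16 places further data conventions in a separate document.

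**The concern.** An imputed event date should agree with what is already known about the patient. It should lie inside the recorded month or year, and after the last date on which the patient was known to be alive or, for progression, progression-free. The rule tests neither condition. The last contact and last tumor evaluation already enter the OS and PFS definitions, but they do not limit the imputed date.

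The exception does not close the gap. It needs a known death date, so it cannot apply when the death date is the incomplete one.

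Survival information gathered remotely at roughly three-month intervals is where partial death dates are plausible. At stake are individual OS and PFS times, and possibly DOR, in a trial planned for 60 evaluable patients. Some of these times would conflict with other dates in the same database, under a rule that presents itself as the most conservative.

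**Working it through.** **The plan's own figure.** Protocol 5.2 defines a cycle as three weeks: 3 × 7 = 21 days, which matches the fallback in SAP 8.10.

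**The rule as a formula.** Let L be the last dose. Let D be the 1st of the known month, or 1 July of the known year if the month is unknown. If D > L, the imputed date is D. Otherwise it is L + 21.

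**Worked cases.** The dates are illustrative assumptions, because the documents give no patient dates and no rate of incomplete dates. OS is the imputed death date minus the first dose date, in days.

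| Case | First dose | Last dose | Last known alive | Death recorded as | Rule gives | OS by rule | OS the record allows |
|---|---|---|---|---|---|---|---|
| A | 16 Jan 2018 | 20 Mar | 25 Mar | March 2018 | 10 Apr | 84 | at most 74 |
| B | 16 Jan 2018 | 20 Mar | 20 Jun | June 2018 | 1 Jun | 136 | at least 155 |
| C | 16 Jan 2018 | 20 Mar | 10 Oct | 2018 | 1 Jul | 166 | at least 267 |
| D | 10 Oct 2018 | 20 Dec | 26 Dec | 2018 | 10 Jan 2019 | 92 | at most 82 |
| E | 1 Jun 2018 | 10 Aug | 9 Sep | 2018 | 31 Aug | 91 | at least 100 |

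- **A.** 1 March is not after 20 March, so the date is 20 March + 21 = 10 April. The last possible March death is 31 March, 74 days after the first dose.
- **B.** 1 June is after 20 March and is accepted, 19 days before the contact of 20 June.
- **C.** 1 July is accepted, 101 days before the contact of 10 October.
- **D.** 1 July fails the check, and 20 December + 21 leaves the recorded year. Any last dose from 11 December onward does so (11 December + 21 = 1 January).
- **E.** 1 July fails, and 10 August + 21 = 31 August is 9 days before the patient was known alive. In general the fallback (21 days) is shorter than the 30-day on-treatment period of SAP 8.4, so a death truly after a day-30 end of treatment that meets the fallback is dated before that point.

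**How often the fallback leaves the month.** With only the day missing, the fallback applies when the event falls in the same calendar month as the last dose. Adding 21 days leaves the month for the last 21 dose dates of every month: 12 × 21 = 252 of 365 dates in 2018 (69%). Over all same-month pairs of last dose and later death in 2018, 2,520 of 5,373 (47%) are imputed outside the true month. In 89% of pairs the imputed death is later than the true one, with a mean error of +10.5 days (range −9 to +20). These counts weight all dates equally. They show the direction of the error, not its expected frequency.

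**Direction.** With only the day missing, the fallback usually lengthens survival (A). With only the year known it can err either way (D, E). The 1st-of-month and 1 July rules, when they place a death before a known contact, shorten survival (B, C).

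**The case against.** **Which paragraph governs.** A death within 30 days of the last dose itself sets the end of treatment (Protocol 6.2, SAP 8.4), so case A could be said to belong to the on-treatment paragraph of SAP 8.10. That paragraph keeps an imputed date only if it precedes treatment start and otherwise uses treatment start. Read literally, it cannot date a death at all. Only the post-treatment paragraph names PFS and OS, and its exception already contemplates deaths within 21 days of dosing. Cases B and C do not depend on this question.

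**The separate conventions document.** It may contain a bound. It was not available, so this stands as a limitation. SAP 8.10 nevertheless states a complete rule without a bound and points to none.

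**Conservatism.** A reader might infer that the whole rule betrays its conservative label. It does not: cases B and C shorten survival, which in a single-arm trial is the cautious direction. Their fault is conflict with recorded data. The charge of working against the stated aim belongs to the fallback where it lengthens survival.

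**The 12-week mark.** A reader might also infer that the fallback moves deaths past 12 weeks and so touches the primary result. The documents do not support that. The schedule counts the first dose as Day 1, so a last dose on Day 64 gives Day 64 + 21 = Day 85, which is exactly 84 days after the first dose, as in case A. A later last dose could pass the mark, but only in the secondary Kaplan-Meier estimate. PFS3 is a yes/no classification. Under SAP 4, patients who progress, die of malignant disease or die of a treatment-related event before the Week 12 evaluation are non-responders. SAP 11.3.1 counts evaluable patients without 12 weeks of follow-up as PFS3 = No.

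**Conclusion.** The rule is wrong as written, and the consequence is small. Because imputed dates are compared only with the last dose, the 21-day fallback can move a death out of its recorded month or year. The 1st-of-month and 1 July defaults can place a death before a documented contact or progression-free scan. In the illustrative cases OS is overstated by at least 10 days (A: 84 against at most 74; D: 92 against at most 82) or understated by at least 9 to 101 days (E, B, C). All these times remain positive and calculable; the fault is inconsistency with the record.

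The effect is confined to secondary OS and PFS and possibly DOR, for which SAP 6.2.2 expects no formal conclusions from comparisons. Few patients are expected to be affected, although the documents give no rate of incomplete dates. PFS3 is essentially unaffected. The conclusion rests on the text of SAP 8.10 and assumes that the unseen conventions document adds no bound.

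**What to change.** Add to the post-treatment paragraph of SAP 8.10:

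*For an incomplete death date, the imputed date is the later of the first day of the known month (or year) and the day after the patient was last known alive, and not later than the end of the known month (or year); the 21-day fallback is not used for deaths. For an incomplete progression date, the imputed date is after the last progression-free tumor assessment, not later than the end of the known month (or year), and not later than the date of death.*

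Deaths and progressions need separate bounds. A last-known-alive bound applied to a progression can leave no valid date: for a progression in June in a patient still alive in October, the lower bound would fall after 30 June.

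With the death rule the cases become: A, 26 March (OS 69 days); B, 21 June (156); C, 11 October (268); D, 27 December (78); E, 10 September (101). Each agrees with the record.

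If the conventions document already holds such bounds, a cross-reference in SAP 8.10 is enough. The cost is a short SAP edit and a small programming change, with no new data and no change to the design.

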8.11. Decimal Places

By default, all numeric results will be rounded to one decimal, except when variables are integer; in that case, they will be reported without decimals, for example, age in years, number of sites, etc. or in the case of p-values and Hazard Ratio values where four decimals will be used.

8.12. Subgroup Analyses

If applicable, specific analyses for different subgroups determined by the following factors will be developed: prior oxaliplatin exposure, tumor primary location: right vs left side tumors, KRAS status, BRAF-like expression, MSI phenotype and other relevant factors determined by the oncologist.

No differentiation by center is planned.

8.13. *Methods for Handling Missing Data*

Missing values will not be included in the calculation of outputs.

8.14. *First Stage Analysis*

A futility analysis will be performed once the first 24 evaluable patients complete the Week 12 (± 5 days) tumor assessment; progress; die due to PD; or discontinue treatment due to unmanageable toxicity (whichever occurs first). If seven patients or more achieve PFS3, then 36 additional patients will be recruited (second stage).

8.15. *Identification of Fixed or Random Effects Models*

Not applicable.

8.16. *Data Analysis Conventions*

All data analysis conventions, data calculations and grouping needed to perform the statistical analysis will be described in a separate document.

9. STATISTICAL SOFTWARE

Medidata Rave® EDC will be used for data entry and clinical data management.

EAST v.6 has been used to calculate sample size.

SAS v.9.4 or superior will be used for all statistical analysis outputs.

I. APPENDIX: TABLES, LISTINGS AND GRAPHS

Summary tables will have source data footnotes that will refer to the relevant listings. The tables' layout may change to adequately accommodate group size as appropriate.

If the number of categories or items does not yield appropriate tabular or graphic representations, detailed listings will be shown instead.

10. Study Patients

Main characteristics concerning inclusion in the study, withdrawal from the study and protocol deviations will be displayed in this section.

10.1. Patient Disposition

Patient disposition analysis will be based in the “All included patients” population.

Table 10.1.1 Number of patients included, treated and evaluable for the main endpoint.

	N	%
Included patients		
Eligible patients*		
Treated patients		
Evaluable patients for efficacy		

(*) Patients meeting all inclusion criteria and not meeting any exclusion criteria.

Listing 10.1.2 Patients who do not meet all inclusion criteria or meet any exclusion criteria.

Patient id.	Criterion number(s) and description

Listing 10.1.3 Screening failures.

Patient	Inclusion/Exclusion criterion not met

Listing 10.1.4 Non-evaluable patients for efficacy.

Patient id.	Reason

Listing 10.1.5 Non-evaluable patients for safety (Non-treated patients).

Patient id.	Reason

Table 10.1.6 Patients accrual by country/institution.

Country/Institution	No. of patients included		No. of patients treated	
	N	%	N	%
Institution 1				
Institution 2				
...				

Table 10.1.7 Relevant study dates.

	Total
Date of first patient's informed consent	
Date of first dose of the first patient	
Date of last patient's informed consent	
Date of first dose of the last patient	
Date of last dose	
Date of last follow-up*	

(*) Last follow-up, examination or procedure before clinical cut-off or study closure.

10.2. Discontinuations

Treatment discontinuation tables and listings will be based on “All treated patients”, whereas study discontinuation tables and listings will be based on “All included patients”.

10.2.1. Treatment discontinuations

Table 10.2.1 Treatment discontinuation.

Reason	N	%
Progressive disease		
Patient refusal to treatment		
Death (due to toxicity)* ¹		
Death (non-treatment-related)* ²		
Investigator's decision* ³		
Treatment-related AE		
Non treatment-related AE		
Other* ³		
Total		

(*¹) Cause of death = Study drug related AE; (*²) Cause of death = Malignant disease, Non study drug related AE or Other; (*³) See [Listing 10.2.2](#).

Listing 10.2.2 Reasons for treatment discontinuation other than progressive disease.

Patient id.	Reason	Last cycle	Comments

When the reason for discontinuation is a study treatment-related adverse event or death due to toxicity, patients will be identified and described in depth in [Listing 10.2.3](#).

Listing 10.2.3 Treatment discontinuation due to AEs.

Patient id.	Last cycle	Preferred term code	AE reported (verbatim)	Grade	Relationship	Onset date	Resolved date	Seriousness criteria

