10.2.2. Study discontinuation

Table 10.2.4 Study discontinuation.

Reason	N	%
Never treated* ¹		
Withdrawal of consent		
Death (due to toxicity)* ²		
Death (non-treatment-related) * ³		
Lost to follow-up		
Other * ⁴		
Total		

(*¹) See [Listing 10.1.5](#); (*²) Cause of death = Study drug related AE or UK relationship; (*³) Cause of death = Malignant disease, Non study drug related AE or Other; (*⁴) Specified in [Listing 10.2.5](#).

Listing 10.2.5 Study discontinuation due to other reason.

Patient id.	Specify

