12.2. Adverse Events

As far as all toxicities are concerned, the NCI-CTCAE v.4 grade will be used wherever an NCI-CTCAE grading exists. Otherwise, the severity will be noted. As a convention, the term «Grade» will always be used. Toxicities will be described according to the worst NCI-CTCAE grade or, for toxicities which do not form the subject of NCI-CTCAE classification, according to the worst severity, as described in NCI-CTCAE.

AEs will be described in this section; treatment-related events (stated as related to the study drug or of unknown relationship) will be tabulated. AEs regardless relationship will be tabulated in two different ways as any AE reported or as treatment emergent AEs (excluding AEs present before drug administration and without increase in severity grade along the treatment).

Type of toxicity and worst grade or severity by cycle and by patient will be summarized according to the Preferred Term coded with MedDRA. Tables will be organized per category of events using System Organ Class of MedDRA.

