12.2.1. Display of Adverse Events

Table 12.2.1 Summary of AEs.

Category*	N (%)
Any AE	
Any drug-related AE	
Any grade 3/4 AE	
Any grade 3/4 drug-related AE	
Any treatment emergent AE* ²	
Any SAE in clinical database	
Any drug-related SAE in clinical database	
Any grade 3/4 SAE in clinical database	
Any grade 3/4 drug-related SAE in clinical database	
Deaths associated with AEs	
Deaths associated with drug-related AEs	
Treatment discontinuations associated with AEs	
Treatment discontinuations associated with drug-related AEs	

(*) Drug-related: AEs drug-related and unknown relationship.

(*²) excluding AEs present before drug administration and without increase in severity grade along the treatment.

Table 12.2.2 Treatment-related AEs. Worst grade by patient.

SOC	Preferred Term	Grade 1		...	Grade 4		All*	
		N	%		N	%	N	%
Blood and lymphatic system disorders	Anaemia Not Otherwise Specified (NOS)							
	...							
	...							
Cardiac disorders	Neuropathy peripheral							
	...							

(*) Any grade.

Table 12.2.3 Treatment-related AEs. Worst grade by cycle.

SOC	Preferred Term	Grade 1		...	Grade 4		All*	
		N	%		N	%	N	%
Blood and lymphatic system disorders	Anaemia NOS							
	...							
	...							
Cardiac disorders	Neuropathy peripheral							
	...							

(*) Any grade.

Table 12.2.4 Adverse Event regardless of relationship. Worst grade by patient.

SOC	Preferred Term	Grade 1		...	Grade 4		All*	
		N	%		N	%	N	%
Blood and lymphatic system disorders	Anaemia NOS							
	...							
	...							
Cardiac disorders	Neuropathy peripheral							
	...							

(*) Any grade.

Table 12.2.5 Adverse Event regardless of relationship. Worst grade by cycle.

SOC	Preferred Term	Grade 1			...	Grade 4		All*	
		N	%	...	N	%	N	%	
Blood and lymphatic system disorders	Anaemia NOS								
	...								
	...								
Cardiac disorders	Neuropathy peripheral								
	...								

(*) Any grade.

Table 12.2.6 Treatment emergent AEs. Worst grade by patient.

SOC	Preferred Term	Grade 1			...	Grade 4		All*	
		N	%	...	N	%	N	%	
Blood and lymphatic system disorders	Anaemia NOS								
	...								
	...								
Cardiac disorders	Neuropathy peripheral								
	...								

(*) Any grade.

Table 12.2.7 Treatment emergent AEs. Worst grade by cycle.

SOC	Preferred Term	Grade 1			...	Grade 4		All*	
		N	%	...	N	%	N	%	
Blood and lymphatic system disorders	Anaemia NOS								
	...								
	...								
Cardiac disorders	Neuropathy peripheral								
	...								

(*) Any grade.

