12.3.2. Deaths

Table 12.3.6 Cause of death.

	N	%
Deaths		
Reason*		
Malignant disease		
Study drug related AE		
Non-study drug related AE		
Other		

(*) Denominator=Number of patients who died.

Listing 12.3.7 Death.

Patient id.	Date of death	Cause	Comments	Autopsy	Number of cycles administered	Date of last infusion	Time on treatment* ¹	Time from last dose* ²

(*¹) Time on treatment: defined as date of last infusion plus 30 days, or date of death or subsequent therapy (whichever comes first) minus date of first infusion. (*²) Time from last dose defined as date of death minus date of last infusion.

Listing 12.3.8 AEs with an outcome of death.

Patient id.	Cycle	Preferred term code	AE reported (verbatim)	Grade	Relationship	Onset date	Date of death	Action

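### A death of unknown relationship counts as toxic in SAP Table 10.2.4 but not in Table 10.2.1, so the same death can be classed both ways in one report

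*SAP*

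**What the plan says.** Five places in the SAP decide whether a death is shown as drug-related.

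- **Table 10.2.1, treatment discontinuation (SAP 10.2.1).** Toxic death is "Cause of death = Study drug related AE". Non-treatment-related death is "Cause of death = Malignant disease, Non study drug related AE or Other". There is also a separate row for other reasons.
- **Table 10.2.4, study discontinuation (SAP 10.2.2).** Toxic death is "Cause of death = Study drug related AE or UK relationship". The footnote for non-treatment-related death lists the same three causes as in Table 10.2.1.
- **SAP 12.2.** In the adverse event tables, "treatment-related events (stated as related to the study drug or of unknown relationship) will be tabulated".
- **Table 12.2.1 (SAP 12.2.1).** The footnote says "Drug-related: AEs drug-related and unknown relationship". This table has a row for deaths associated with drug-related AEs.
- **Table 12.3.6, cause of death (SAP 12.3.2).** The causes are malignant disease, study drug related AE, "Non-study drug related AE" and other. Unknown relationship has no row.

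The two disposition tables also use different populations. SAP 10.2 bases treatment discontinuation on all treated patients, "whereas study discontinuation tables and listings will be based on" all included patients.

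Protocol 8.4.9 allows three causality values for an SAE: Y, N and Uk. Uk is reserved for special situations in which the Investigator lacks the information to decide.

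**The concern.** Two tables a page apart use the same row label with different content, and the only difference is where unknown relationship goes. A reader who compares the toxic-death rows would expect one definition. The number of toxic deaths in a single-arm phase II trial is small and closely read, so a difference of one is noticeable and would have to be explained.

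There is a second consequence. SAP 10.2.1 promises an in-depth description in Listing 10.2.3 when treatment stopped because of a treatment-related AE or a toxic death. A death of unknown relationship that Table 10.2.1 does not class as toxic might be left out of that listing, although SAP 12.2 counts the underlying event as treatment-related.

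**Working it through.** The plan states no figure to reproduce. The check compares the definitions and then counts.

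**Step 1. Where each rule puts a death of unknown relationship**

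| Place in SAP | Unknown relationship named? | Resulting class |
|---|---|---|
| Table 10.2.1 | No | Probably non-treatment-related, through Other |
| Table 10.2.4 | Yes | Due to toxicity |
| SAP 12.2 | Yes | Treatment-related |
| Table 12.2.1 | Yes | Drug-related |
| Table 12.3.6 | No | Unstated; Other is the residual row |

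Three of the five places class it as drug-related by name. None classes it as unrelated by name.

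**Step 2. Can the populations explain the difference?** No. Included patients who were never treated cannot die of drug toxicity, so moving from treated to included patients adds no toxic deaths.

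**Step 3. Effect on the counts.** Let R be the deaths judged related and U the deaths of unknown relationship, all ending both treatment and study.

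- Toxic deaths in Table 10.2.1 = R
- Toxic deaths in Table 10.2.4 = R + U
- Difference = (R + U) − R = U

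| R | U | Table 10.2.1 | Table 10.2.4 | Difference |
|---|---|---|---|---|
| 1 | 0 | 1 | 1 | 0 |
| 0 | 1 | 0 | 1 | 1 |
| 1 | 1 | 1 | 2 | 1 |
| 2 | 1 | 2 | 3 | 1 |

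**Step 4. How likely is U ≥ 1?** The documents give no rate, so the rates p below are assumptions. P(U ≥ 1) = 1 − (1 − p)^n, with n set to the planned evaluable numbers of 24 (stage 1) and 60 (both stages) for illustration only.

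| Assumed p | n = 24 | n = 60 |
|---|---|---|
| 0.1% | 2.4% | 5.8% |
| 0.5% | 11.3% | 26.0% |
| 1% | 21.4% | 45.3% |
| 3% | 51.9% | 83.9% |

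The range is wide. The discrepancy is possible at any of these rates and certain at none.

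**Step 5. After alignment.** If Table 10.2.1 also includes unknown relationship, both tables count R + U and the difference due to wording is zero.

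**The case against.** The strongest reply is that this is a wording mismatch in disposition tables and that the deaths themselves are reported in SAP section 12. Table 12.2.1 counts unknown as drug-related, Listing 12.3.8 shows the relationship of each fatal event, and Listing 10.2.2 gives the reason for every discontinuation other than progression. A death of unknown relationship would therefore be visible somewhere. That stands, and it keeps the point minor. It does not remove the contradiction between the tables.

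A second reply is that the two death footnotes of Table 10.2.1 together match the four causes in Table 12.3.6, so Table 10.2.4 may be the exception. The match is real. But SAP 12.2 and Table 12.2.1 side with Table 10.2.4, so the SAP's prevailing convention is to count unknown as related. One could read that convention into Table 10.2.1 silently, but Table 10.2.4 found it necessary to name unknown separately, which argues against doing so. SAP 8.16 places analysis conventions in a separate document, which may resolve this but is not available.

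A third reply is that the tables record different events and need not agree. A patient who stops treatment for progression and later dies of toxicity is a toxic death only in Table 10.2.4. This is correct. A shared definition would let a reader attribute any remaining gap to timing.

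**Conclusion.** The inconsistency is real and minor. As written, Table 10.2.1 would probably class a death of unknown relationship as non-treatment-related, while Table 10.2.4 classes it as toxic and Table 12.2.1 counts a fatal AE of unknown relationship as drug-related. The gap between the two disposition tables is U deaths, provided those deaths end both treatment and study. The conclusion assumes that Other acts as the residual class and that no separate conventions document overrides the footnotes.

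A reader might infer more than the documents support.

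- **That such a death has no place in Table 10.2.1.** It is not named, but Other can absorb it. The problem is the opposite class, not a missing one.
- **That the report will necessarily show two toxic-death counts.** This wording produces a gap only if at least one death of unknown relationship ends treatment.
- **That a fixed percentage of 60 is at stake.** Sixty is the evaluable target. The tables are based on treated and included patients, whose numbers are not fixed in advance.
- **That PFS3 or its denominator changes.** SAP 4 defines evaluability separately, and nothing links it to these footnotes.

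**What to change.** 1. Add unknown relationship to footnote 1 of Table 10.2.1, so that it matches the toxic-death footnote of Table 10.2.4. Such a death would then also trigger Listing 10.2.3.
2. In Table 12.3.6, apply the same convention to the study-drug-related row, or add a separate row for unknown relationship. A separate row shows more, because the reader can see R and U and add them.
3. Check that Tables 10.2.1, 10.2.4, 12.2.1 and 12.3.6 then rest on one definition.

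The change should stop at these tables. Making unknown relationship automatically treatment-related in SAP 4 would alter an analysis-set rule. It would also go beyond Protocol 8.4.7, where related means the Investigator's Y and the Sponsor has only the option of treating Uk events as related.

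The cost is one footnote and one row or footnote in the SAP table shells, with no new data and no change to the design. The downside is that the toxic-death count in Table 10.2.1 may be slightly higher, by the number of deaths of unknown relationship that end treatment.
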